##### a) Impact on Pain

Measured through the following question: "On a scale of 0 to 10, where 0 is no pain and 10 the worst pain imaginable, how would you rate your pain in the last 24 hours?"

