##### c) Interest in undergoing surgery

Measured through the following question: "On a scale of 0 to 10, where 0 is not at all and 10 is extremely interested, how interested are you in undergoing back surgery in the next 12 months"?

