##### d) Medication consumption

Measured through the following questions:

- i. "Are you taking any medication for your low back pain?";
- ii. "If yes, are you taking opioids for your low back pain?";
- iii. "If yes, on how many days in a week, on average, are you taking medication for your low back pain"

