## **10. INCLUSION/EXCLUSION CRITERIA**

### **10.1 Inclusion Criteria**

- a) Subjects aged between 18 and 80 years of age at enrolment
- b) Reporting intermittent or persistent low back pain for at least 12 weeks, and/or present at least 50% of the time in the past 6 months
- c) Ability to understand complex motor tasks

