## SH-RCT-LBP-US-01 Clinical Investigation Protocol

respectively. These trackers enable precise movement quantification, feeding the mobile app, which guides the patient through the session, providing video and audio instructions before each exercise, as well as real-time audio and video biofeedback during the exercise. On the other end, the clinical teams are allowed to remotely monitor results and prescribe/edit exercise sessions through a web-based portal.

The exercise component will follow the protocol outlined in **Annex 2**, which can however be adapted by the physical therapist to the specific needs of the participant. Participants will be asked to start with three 20 min sessions per week, building gradually to three 30 min sessions per week. Participants will not be excluded from the study in case of lower adherence. Participants in this group will be considered as dropouts if they: a) choose to abandon the study; b) do not engage in any exercise session for at least fourteen consecutive days.

The educational component will be delivered automatically through a smartphone app (available for iOS and Android), and will take the form of small educational texts that will be released periodically to the participant. This component is not mandatory per protocol, but metrics on user engagement will be measured.

The CBT program will take the form of a self-paced program consisting of written and pre-recorded audio materials. An email will be sent weekly by the physical therapist to the participant, during the 8 weeks of the program. Each email will contain an introductory text describing the objectives for that week, as well as a link to that week's audio session and a PDF attachment with self-guided exercises. The CBT component is not mandatory per protocol, but metrics on user engagement will be measured.

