### 15. ASSESSMENTS AND SPECIFIC DATA COLLECTION

Patients will be assessed at baseline, 4 and 8 weeks. All questionnaires will be collected through the EDC system. These will need to be filled within 5 consecutive days. To promote compliance with this schedule, whenever the deadline is approaching, automatic email reminders will be sent to participants. Participants will be excluded from the study for protocol breach in case they don't fill in the assessment forms.

Regarding the **baseline assessment**, participants will be asked to complete the survey before the start of the program. This assessment will include all the information pertaining to the primary and secondary outcomes, as well as the following information:

- a) date of birth
- b) gender
- c) height & weight
- d) body mass index
- e) formal education (years of schooling)
- f) job type
- g) baseline physical activity level
- h) previous back surgery (> 3 months ago)
- i) risk factors: working status, smoking status

For the **4- and 8-week assessment**, participants will be required to complete the questionnaire within a 5-day window beginning at the start of week 4 and 8. These assessments will include all the information pertaining to the primary and secondary outcomes. Physical activity will be measured only at baseline and 8 week assessment.

For participants on the digital group, engagement and usage metrics of the educational and CBT components will also be collected automatically.

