## 17. RISKS AND BENEFITS

## SH-RCT-LBP-US-01 Clinical Investigation Protocol

Participants in this clinical study will be allocated to one of two treatment groups. In any case, they will be receiving an evidence-based treatment program tailored to their condition, overseen by physicians and physical therapists.

Participants in the digital care program will be performing the exercise component using a certified medical device for its intended purpose. Therefore, participants are not running additional risks by participating in this study.

Exercise programs can, however, be associated with temporary pain or discomfort. In the digital care group, pain and fatigue scores will be asked at the end of each session, and this information is relayed to the physical therapist assigned to the participant, who will contact the patient in case of excessive pain or fatigue. In the conventional PT group, sessions will be performed under direct supervision from a physical therapist. In any case, both participants and physical therapists will be instructed to contact the study investigators in case of an adverse event.

As to the benefits, by participating in this study, participants may experience reduction in pain, improvement in function, mood and general well-being. However, the effects may vary from person to person, and therefore substantial improvements cannot be guaranteed.

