Standing trunk extention	2 sets of 14 repetitions (alternating)		3 sets of 10 repetitions (alternating)
Pelvic anterior-posterior tilt	2 sets of 14 repetitions (alternating)	2 sets of 14 repetitions (alternating)	
Pelvic side tilt	2 sets of 14 repetitions (alternating)	2 sets of 14 repetitions (alternating)	
Estimated Training Time	28 min	28 min	31 min

Low Back Pain Program – Final Phase			
Week 8			
Goals			
Increase external load Explosion / Power exercises Return to all daily activities Maximum complexity on the exercises Specific activities training Focus on education and prevention of chronic			
Intervention			
Daily Digital Therapist Sessions 8-week Remote Assessment			
SWORD exercises	Mobility / Endurance Session A	Mobility / Endurance Session B	Strength Session
Cat-camel	2 sets of 16 repetitions (alternating)	2 sets of 16 repetitions (alternating)	
Child's pose	2 sets of 1 repetitions (alternating)	2 sets of 1 repetitions (alternating)	2 sets of 1 repetitions (alternating)
Prone press ups	2 sets of 1 repetitions (alternating)	2 sets of 1 repetitions (alternating)	2 sets of 1 repetitions (alternating)
Isometric cat pose	2 sets of 1 repetitions (alternating)		
Plank			2 sets of 1 repetitions (alternating)
Plank with trunk rotation			2 sets of 8 repetitions (alternating)
Plank and hand walking			2 sets of 4 repetitions (alternating)
Side plank			1 sets of 4 repetitions (alternating)

Isometric side plank			1 sets of 2 repetitions (alternating)
Sitting trunk flexion			
Sitting trunk flexion with rotation			
Sitting trunk rotation		1 set of 10 repetitions (alternating)	
Sitting trunk extension			
Sitting trunk side bend			
Siting trunk extension with rotation			
Standing trunk flexion		3 sets of 12 repetitions (alternating)	3 sets of 8 repetitions (alternating)
Standing trunk flexion with rotation	3 sets of 14 repetitions (alternating)		3 sets of 12 repetitions (alternating)
Standing trunk rotation	3 sets of 14 repetitions (alternating)		3 sets of 12 repetitions (alternating)
Standing trunk side bend	3 sets of 14 repetitions (alternating)	3 sets of 16 repetitions (alternating)	3 sets of 12 repetitions (alternating)
Standing trunk extention		3 sets of 12 repetitions (alternating)	3 sets of 8 repetitions (alternating)
Pelvic anterior-posterior tilt	2 sets of 14 repetitions (alternating)	2 sets of 16 repetitions (alternating)	

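### The 0–10 pain item does not name the low back, so participants answering it as written may rate pain at another site

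*Combined protocol and SAP*

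**What the plan says.** Section 8.2 a) prints the pain question in full. It is a 0–10 rating that asks "how would you rate your pain in the last 24 hours". It names no body site, and no preamble or instruction elsewhere in the document supplies one.

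The neighbouring questions are specific. Section 8.2 c) asks "how interested are you in undergoing back surgery in the next 12 months". Section 8.2 d) opens with "Are you taking any medication for your low back pain", and its two follow-up questions repeat the site.

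Section 10.1 admits ages 18 to 80 and includes people "Reporting intermittent or persistent low back pain for at least 12 weeks". The exclusions in Section 10.2 cover pregnancy, recent spinal surgery, infection, cancer, neurological disease and similar conditions. A painful joint elsewhere is not on the list, although criterion f) would remove anyone whose other disorder rules out 20 minutes of light to moderate activity. Recruitment is from an outpatient musculoskeletal clinic (Section 11).

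Under Section 15 the follow-up forms are completed "within a 5-day window beginning at the start of week 4 and 8", while the programme is still running.

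**The concern.** A pain score in a low back pain trial should measure low back pain. As printed, the question lets a participant report whichever pain is most prominent. Other-site pain is plausible in this population and is not screened out.

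Randomisation should balance such pain between arms on average, so the main consequence is not bias. The score carries variation unrelated to the condition under study, and a true difference in back pain may appear smaller than it is. Section 6 expects the digital programme to do at least as well as conventional physical therapy, and an item that blurs differences makes the arms look more alike. No analysis can later separate back pain from other pain within one unsited number.

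**Working it through.** **1. The plan's own figure.** The only sample size in the plan is for the ODI (Section 9): SD 17.83, difference 10, two-sided 0.05, power 80%. The allocation ratio is not stated, so 1:1 is assumed.

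- Normal approximation: n per arm = 2 × (1.960 + 0.842)² × 17.83² / 10² = 49.9, so 50 per arm and 100 in total.
- t-test version: 50.88, so 51 per arm and 102 in total, as stated.

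The pain item plays no part in this calculation. No SD, target difference or power is given for pain.

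**2. Wording side by side.**

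| Item | Site named? |
|---|---|
| Pain, 8.2 a) | No |
| Interest in surgery, 8.2 c) | Back |
| Medication, 8.2 d), three questions | Low back |

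**3. Effect on the between-arm difference.** Let D be the true difference in back pain, f the fraction of participants who rate another site, and E the between-arm difference in that other pain.

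Observed difference = (1 − f) × D + f × E

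- If the arms do not differ in their effect on other-site pain (E = 0), the difference shrinks to (1 − f) × D.
- E need not be zero. The digital arm includes pain education and cognitive behavioural therapy. The conventional arm includes manual therapy and hip, hamstring and gluteal stretches. Either could affect pain elsewhere.
- The documents give neither f nor E. Purely as an assumption, f = 0.1 to 0.3 with E = 0 shrinks the difference by 10% to 30%.
- A separate illustration in terms of noise: if a share r = 0.1 to 0.3 of the item's variance came from other sites (assumed), the standardised effect would be multiplied by √(1 − r) = 0.95 to 0.84. The N needed for this outcome would be multiplied by 1/(1 − r) = 1.11 to 1.43.

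Neither range has support in the documents. They show the form of the effect, not its size.

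**4. Whether exercise soreness adds an arm difference.** Section 17 accepts that "Exercise programs can, however, be associated with temporary pain or discomfort". Suppose soreness adds s points on an exercise day and the form falls on a random day. The mean shift is then s × (exercise days per week) / 7.

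- Digital, Section 14.1: "three 20 min sessions per week, building gradually to three 30 min sessions per week", so 3/7 = 43% of days. The Annex 2 tables are headed "Daily Digital Therapist Sessions", which would be 7/7 = 100%. These two places contradict each other and must be reconciled.
- Conventional, Section 14.2: two clinic sessions a week, so 2/7 = 29%. Annex 3 also tells patients to continue the exercises at home and gives no frequency. With h further exercise days the figure is (2 + h)/7.

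The arm difference (digital minus conventional) is s × (1 − h)/7 on the Section 14.1 schedule and s × (5 − h)/7 on the Annex 2 schedule. With s assumed to be 0.5 to 2 points:

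| | h = 0 | h = 1 | h = 2 |
|---|---|---|---|
| Section 14.1 | 0.07 to 0.29 | 0 | −0.07 to −0.29 |
| Annex 2 | 0.36 to 1.43 | 0.29 to 1.14 | 0.21 to 0.86 |

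The documents give neither s nor h and contradict themselves on digital frequency, so neither the size nor the sign is fixed.

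**5. Whether a 7-day average would cure it.** Averaged over a week, the shift is again s × (exercise days)/7, the same mean as for a randomly timed 24-hour rating. Longer recall smooths good and bad days but leaves any mean soreness difference in place.

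**The case against.** The best defence is context. Participants enrol because of low back pain, in a low back pain trial, and meet this question among others that name the back. Many will assume that the back is meant. That stands: the wording permits an answer about another site but does not show that anyone will give one. It does not justify leaving the site out, because the plan contains no instruction to that effect and its own neighbouring questions do not rely on context.

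Two stronger readings are tempting.

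- **That the 24-hour window biases the comparison because the digital arm exercises more often.** A reader might infer this from three sessions a week against two. The inference ignores conventional-arm home exercise in Annex 3 and the conflicting frequency in Annex 2, so an unequal effect is possible but not established.
- **That 24 hours is the wrong recall period because intermittent pain qualifies for entry.** A participant may indeed score zero on a good day, but such days are expected to balance between randomised arms and are noise. Longer recall brings recall error of its own, and the documents give no data for weighing the two. This is a trade-off rather than a fault.

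This is also one of several secondary outcomes, for which the plan states no order of importance.

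**Conclusion.** The wording defect is certain: the item omits the site, and its neighbours do not. The consequence is a possibility, namely added noise in this secondary outcome and perhaps a diluted between-arm difference. It depends on some participants having notable pain elsewhere and rating it, and dilution further depends on that pain differing less between the arms than back pain does. The documents allow the first condition and are silent on how often it would occur, so no size can be given.

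The point does not affect the primary outcome or its sample size, and it does not support a claim of bias between arms. It is a modest point, worth acting on because the correction is so cheap.

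**What to change.** In Section 8.2 a) and on the data-capture form, insert the words low back before the word pain, keeping the 0–10 scale and the 24-hour recall. Use exactly this wording at baseline, 4 and 8 weeks in both arms.

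The cost is one form edit, with slightly less comparability with any other data collected using the unsited question. The document does not say whether enrolment has begun. The change should be made before data collection. If that is no longer possible, the wording must be applied consistently so that no participant's change score mixes two versions of the question.

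A longer averaging period, such as 7 days, is optional. It would reduce day-to-day noise from intermittent pain, but it should not be presented as removing an arm difference from exercise soreness.

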##### b) Impact on work productivity and activity impairment

Measured through Work Productivity and Activity Impairment Questionnaire: Specific Health Problem v2.0 (WPAI:SHP)

##### c) Interest in undergoing surgery

Measured through the following question: "On a scale of 0 to 10, where 0 is not at all and 10 is extremely interested, how interested are you in undergoing back surgery in the next 12 months"?

##### d) Medication consumption

Measured through the following questions:

- i. "Are you taking any medication for your low back pain?";
- ii. "If yes, are you taking opioids for your low back pain?";
- iii. "If yes, on how many days in a week, on average, are you taking medication for your low back pain"

##### e) Impact on fear avoidance beliefs

## SH-RCT-LBP-US-01 Clinical Investigation Protocol

Measured by: Patient-reported questionnaire (Fear Avoidance Beliefs Questionnaire- FABQ)

### **f) Impact on anxiety and depression**

Measured by the General Anxiety Disorder-7 scale and Patient Health Questionnaire-9 scale

### **g) Patient engagement**

Measured through: g.1) adherence to exercise sessions; g.2) drop-out rates; g.3) treatment intensity (i.e. total number of exercise minutes)

### **h) Patient satisfaction**

Measured through the Net Promoter Score

### **i) Impact on physical activity levels**

Measured through the International Physical Activity Questionnaire- Short Form.

## **9. SAMPLE SIZE ESTIMATION**

Sample size estimation calculations were performed taking into consideration the primary outcome measure – The Oswestry Disability Index (ODI). In the absence of similar studies, the calculations were made considering the study by Stankovic et al. (2012). This was a large study (n=160 patients), which compared two different rehabilitation protocols for CLBP and which used the same primary outcome as the present study. In this study, the standard deviation of the ODI at baseline was 17.83 points. A Minimal Clinically Important Change (MCIC) of 10 points was considered, based on the study by Ostelo et al. Considering a power of 80% and a two-sided 0.05 significance level, 102 individuals will be necessary to detect a 10-point difference between the two groups.

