### 8. STUDY OUTCOMES

#### 8.1 Primary Outcome

Impact on functional disability measured through the Oswestry Disability Index score (patient reported outcome measure) between baseline and 8 weeks.

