## 16. STATISTICAL ANALYSIS PLAN

To assess differences in clinical and demographic variables of the patients allocated to the two study groups, independent samples t test or Mann–Whitney U test will be used for quantitative variables. For categorical variables, Chi-square test or Fisher's exact test will be used.

Outcome analysis will be performed using both an intention to treat analysis and a per-protocol analysis.

The overall impact of the intervention on the primary and secondary outcomes will be assessed considering both the results at the 12-week assessment as well as change from baseline.

Differences between interventions will be evaluated using independent samples t test or Mann–Whitney U test. For non-normally distributed variables, the magnitude of the difference in the medians will be assessed using Hodges-Lehman estimator. Additionally, a repeated measures ANOVA will also be performed, with group as an independent factor and time as a within-subjects factor. When necessary, logarithmic transformation will be performed to obtain normally distributed variables. In all analysis, a significant level of 0.05 will be considered.

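### The power rests on a baseline ODI standard deviation: for change from baseline, 80% needs a correlation of at least 0.5, and no planned analysis uses baseline ODI as a covariate

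*Combined protocol and SAP*

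**What the plan says.** Section 9 takes its variability from an earlier rehabilitation study of 160 patients, in which "the standard deviation of the ODI at baseline was 17.83 points". The error rates follow: "Considering a power of 80% and a two-sided 0.05 significance level". The conclusion is that "102 individuals will be necessary to detect a 10-point difference between the two groups". Section 9 gives no SD at 8 weeks, no SD of change and no correlation between baseline and follow-up.

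Section 8.1 defines the primary outcome as "Impact on functional disability measured through the Oswestry Disability Index score (patient reported outcome measure) between baseline and 8 weeks". Section 16 assesses outcomes "considering both the results at the 12-week assessment as well as change from baseline". The between-group method is stated as "Differences between interventions will be evaluated using independent samples t test", with the Mann–Whitney U test as the alternative. A repeated-measures ANOVA with group and time is added. None of these models has a covariate, and none is named as primary.

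Section 15 places ODI in the baseline assessment, so a baseline value is planned for every participant. Section 13 randomises in permuted blocks of 6 and mentions no stratification by baseline ODI.

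**The concern.** The SD in a power calculation should belong to the variable that is tested. A change score has a different SD from a single score, and how different depends on how strongly the two measurements correlate. If they correlate weakly, the change test has less power than Section 9 states.

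There is a second, related loss. A baseline measurement of the primary outcome is usually the most useful covariate a trial has. The plan collects it, but uses it only by subtraction (the change score) or as one time level of the outcome (the ANOVA). A regression adjustment would be more precise at no cost in data. It would also adjust for chance imbalance in baseline ODI, against which the allocation scheme offers no protection.

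**Working it through.** **Inputs from the documents.** Difference 10 points, SD 17.83, two-sided 0.05, power 80%, N = 102 (Section 9). Two groups (Section 13).

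**Assumptions.** Allocation 1:1, which is not stated. 51 analysed per arm, so no dropout. SD at baseline (s0) and SD at 8 weeks (s8) both 17.83, unless varied below. The correlation r is not in the documents, so it runs from 0.3 to 0.7. Section 16 names a 12-week assessment where Sections 8.1 and 15 end at 8 weeks; the end value is taken here as the 8-week one.

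**Step 1: the plan's own figure.** By the normal approximation, n per arm = 2 × (1.960 + 0.842)² × 17.83² / 10² = 49.9, so 50 per arm and 100 in total. The non-central t calculation gives 50.88, so 51 per arm and 102 in total. Section 9 is reproduced exactly. Power at 51 per arm is 80.1%.

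**Step 2: formulas.**
- SD of change = sqrt(s0² + s8² − 2·r·s0·s8), which is 17.83 × sqrt(2(1 − r)) when the SDs are equal. It equals 17.83 when r = 0.5, and is larger below 0.5 and smaller above.
- ANCOVA residual SD = s8 × sqrt(1 − r²), which is 17.83 × sqrt(1 − r²) when the SDs are equal.

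**Step 3: results with equal SDs** (non-central t, 51 per arm; the one degree of freedom for the covariate is ignored).

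| r | SD of change | Power, change | N for 80%, change | ANCOVA SD | Power, ANCOVA | N for 80%, ANCOVA |
|---|---|---|---|---|---|---|
| 0.3 | 21.10 | 65.9% | 142 | 17.01 | 83.7% | 94 |
| 0.4 | 19.53 | 72.6% | 122 | 16.34 | 86.4% | 86 |
| 0.5 | 17.83 | 80.1% | 102 | 15.44 | 90.0% | 78 |
| 0.6 | 15.95 | 88.0% | 82 | 14.26 | 93.9% | 66 |
| 0.7 | 13.81 | 95.2% | 62 | 12.73 | 97.5% | 54 |

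The unadjusted 8-week comparison has 80.1% power at every r. The difference detectable with 80% power scales with the SD. For ANCOVA it is about 10 × 15.44 / 17.83 = 8.7 points at r = 0.5 and 10 × 12.73 / 17.83 = 7.1 points at r = 0.7.

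**Step 4: unequal SDs.** The change SD equals 17.83 when r = s8 / (2·s0). For s8/s0 from 0.8 to 1.2, this break-even runs from 0.40 to 0.60. The unadjusted end-value test also depends on s8: its power is 93.9%, 87.6%, 72.2% and 64.7% at ratios 0.8, 0.9, 1.1 and 1.2. ANCOVA at r = 0.5 gives 83.8% at ratio 1.1 and 77.0% at 1.2. It does not guarantee 80%, but it does better than the end-value test in both cases.

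**Step 5: why ANCOVA cannot lose in large samples.** The end-value variance exceeds the ANCOVA variance by r²·s8². The change-score variance exceeds it by s0² + s8² − 2·r·s0·s8 − s8²(1 − r²) = (s0 − r·s8)². Neither quantity can be negative.

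**The case against.** The best defence is that nothing in Section 9 is miscalculated. It powers a 10-point difference between groups without saying that the difference is in change scores. Section 16 does plan an unadjusted t test on end values, and for that test 102 is right if the 8-week SD is 17.83. Unadjusted comparisons are valid in a randomised trial, so baseline adjustment is a matter of efficiency. All of this stands.

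Three stronger readings are tempting, and the documents support none of them.

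- *The trial is underpowered.* That needs an r below the break-even, and the documents give no r. At r above 0.5 with equal SDs, the baseline SD is conservative for change.
- *The 80% holds for change only at r exactly 0.5.* Power is about 80% there and higher at every larger r. The threshold itself assumes equal SDs at the two times.
- *Baseline ODI is ignored.* It enters the change score by subtraction and the ANOVA as a level of the outcome. What is missing is its use as a covariate.

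The case for ANCOVA also has limits. It adjusts for imbalance in baseline ODI, not in other prognostic factors. A mixed model that adds week 4 is an alternative rather than an equivalent, because it uses more data and handles missing values differently.

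What the defence does not answer is that Section 16 tests change as well as end value and names neither as primary. The stated 80% is therefore not tied to one defined test, and a more precise analysis of data already planned is left out.

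**Conclusion.** The point holds as a gap in the justification of power and a free gain in precision, not as an error in N. The sample size of 102 is correct for an unadjusted t test on a variable with SD 17.83. For change from baseline, with equal SDs and 51 analysed per arm, the stated power needs r of at least 0.5; across r = 0.3 to 0.7 it runs from 66% to 95%. ANCOVA over the same range gives about 84% to 98%, and its large-sample variance is never above that of either unadjusted comparison. The size of the gain depends on r and on the 8-week SD, both assumed here. Its direction does not. Losses to follow-up would lower all of these figures.

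**What to change.** In Section 16, name one primary analysis: ANCOVA of 8-week ODI on arm, with baseline ODI as covariate. A baseline-adjusted mixed model that also uses week 4 would be an acceptable alternative. Report the adjusted difference with its 95% confidence interval, and keep the unadjusted tests and the repeated-measures ANOVA as sensitivity analyses.

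In Section 9, state which variable the SD of 17.83 is meant to describe, and show power for the chosen analysis over an assumed range of r, and preferably of the 8-week SD.

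The cost is rewording Sections 9 and 16. No new data, visits or participants are needed, and N can stay at 102 as far as this point goes.

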## SH-RCT-LBP-US-01 Clinical Investigation Protocol

continuously rising, and opioid misuse is an issue of great concern globally, identifying effective nonopioid alternatives for CLBP is of paramount importance.

Further compounding this problem, from the patients who are directed to PT, almost half give up after just 4 sessions, and only 30% complete their programs.

In this context, new ways of delivering care are much needed. Crucially, these need to: a) address the three pillars of care to achieve good and sustained clinical outcomes; b) overcome barriers to access; c) ensure patients are engaged throughout the programs; d) be scalable and cost-efficient.

Thus, SWORD Health has developed a digital care program to address these needs.

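### The sample size of 102 makes no allowance for missing 8-week ODI data, so if 102 is the number randomised, the stated 80% power assumes no loss

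*Combined protocol and SAP*

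**What the plan says.** Section 9 bases the sample size on the primary outcome, the Oswestry Disability Index (ODI). It takes the SD from a published comparison of two rehabilitation protocols ("the standard deviation of the ODI at baseline was 17.83 points") and a 10-point difference from a published minimal important change. It concludes: "Considering a power of 80% and a two-sided 0.05 significance level", "102 individuals will be necessary to detect a 10-point difference between the two groups". It gives no expected loss, and the supplied text contains no larger enrolment target.

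Other sections anticipate loss:

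- Section 8.2(g) makes drop-out rates a secondary outcome.
- Section 14.1 defines dropout in the digital arm ("Participants in this group will be considered as dropouts if they" leave by choice or go fourteen consecutive days without a session). Section 14.2 has a parallel rule based on four consecutive missed sessions.
- Section 15 sets assessments at baseline, 4 and 8 weeks, allows 5 days for the forms and sends reminders. Of those who do not fill in the forms it says: "Participants will be excluded from the study for protocol breach".

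Section 16 plans intention-to-treat (ITT) and per-protocol analyses. It defines neither set and gives no method for missing data. The group comparison is a t test or Mann–Whitney test, with a repeated measures ANOVA in addition.

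**The concern.** A sample size with no margin sits beside a rule that removes participants from the study. Each lost 8-week ODI takes the unadjusted comparison below its stated power, and Section 15 may create losses that need not happen. A participant who skips the 4-week form could be excluded although an 8-week ODI could still be obtained.

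What is at stake is how a non-significant result is read. Section 6 expects the digital program to do at least as well as conventional PT, so a null result may be taken as support, and the stated 80% power would lend it weight. If the power is lower, that weight is not earned.

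**Working it through.** **Inputs.** From Section 9: difference δ = 10, SD σ = 17.83, two-sided α = 0.05, power 80%, total 102. From Section 13: two groups in blocks of 6, with no ratio stated; I assume 1:1, so 51 per arm. From Section 16: independent samples t test. From Section 8.1: the outcome is at 8 weeks. The loss rate is not in the documents, so it is an assumed range, taken as equal in the two arms.

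**Reproducing 102.** The normal approximation gives n per arm = 2(1.96 + 0.8416)² × 17.83² / 10² = 49.9, so 50 per arm or 100 in total. The t test (non-central t) needs 50.88 per arm, so 51 per arm or 102 in total. The match is exact, so no allowance for loss is hidden in the figure.

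**No margin.** With 51 per arm the non-centrality is 10 / (17.83 × √(2/51)) = 2.83 and power is 80.1%. With 51 and 50 it is 79.7%.

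**Power if 102 are randomised and a proportion d has no 8-week ODI.** Analysed n per arm = 51(1 − d).

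| Loss d (assumed) | n per arm | Power, unadjusted t test |
|---|---|---|
| 0% | 51.0 | 80.1% |
| 5% | 48.5 | 78.0% |
| 10% | 45.9 | 75.7% |
| 15% | 43.4 | 73.3% |
| 20% | 40.8 | 70.6% |

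**Effect of adjusting for baseline ODI.** If r is the correlation between baseline and 8-week ODI, the residual SD is 17.83 × √(1 − r²). At r = 0.5 this is 17.83 × 0.866 = 15.44. Power at 20% loss (40.8 per arm), with r assumed:

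| r | Residual SD | Power at 20% loss |
|---|---|---|
| 0.3 | 17.01 | 75% |
| 0.4 | 16.34 | 78% |
| 0.5 | 15.44 | 82% |
| 0.6 | 14.26 | 88% |

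At 20% loss, adjustment raises power above the unadjusted 71% at each of these correlations, and restores 80% or more at r = 0.5 and 0.6.

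**The case against.** **Section 9 does not say that 102 means randomised.** This stands as an ambiguity. If 102 is the number analysed, the 80% is right and an enrolment target is missing: 102 / 0.9 gives 114 at 10% loss and 102 / 0.8 gives 128 at 20%. Either way Section 9 needs an edit, but only on the randomised reading is the power overstated.

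**Treatment dropout is not outcome loss.** This also stands. Someone who stops exercising can still complete the ODI, Section 14.1 keeps participants with low adherence in the study, and Section 16 plans an ITT analysis. A reader might infer from the dropout definitions that those participants are lost to the primary analysis; the documents do not say so. The loss that counts is a missing 8-week ODI or exclusion under Section 15.

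**The background figure is not this trial's loss.** Section 1 says of patients directed to PT that "almost half give up after just 4 sessions, and only 30% complete their programs". It is tempting to read that as expected attrition and conclude that power collapses. It describes completion of treatment in routine care, not outcome collection here, and nothing above uses it.

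**Section 15 does not clearly exclude for lateness.** It sets a 5-day window and excludes those who do not fill in the forms; whether a late form counts is not stated. A participant with no 8-week form has no 8-week ODI in any case, so the rule adds loss mainly through a missed 4-week form.

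**Power might not be below 80%.** Section 16 also analyses change from baseline. With equal SDs, the SD of change is 17.83 × √(2(1 − r)), and power at 20% loss is 63%, 71%, 80% or 90% for r = 0.4, 0.5, 0.6 or 0.7. So the shortfall is conditional on an analysed SD of 17.83. The plan, however, makes no such argument, and Section 9 offers 17.83 as its SD.

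**Power to detect 10 points is not evidence for an at-least-as-good claim.** True. Restating it makes the quoted figure honest but does not supply that evidence.

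**Conclusion.** The concern holds in a limited form. Section 9's arithmetic is correct, but 102 is the bare requirement. If 102 are randomised, 80% power for an unadjusted comparison with SD 17.83 requires every participant to contribute an 8-week ODI. The shortfall is about 2 percentage points at 5% loss and about 9 at 20%. These rest on assumed loss rates equal in the two arms, 1:1 allocation and the t test.

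The documents do not show that the trial will be badly underpowered, since they give no loss rate. The supportable finding is an unqualified power figure, joined to an exclusion rule that could cause avoidable loss. It should be corrected, but it does not undermine the design.

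**What to change.** 1. **Section 9.** State that 102 is the number randomised, give the expected proportion without an 8-week ODI, and quote the power at that loss in place of an unqualified 80%. For example, if 10% loss is expected, the unadjusted power is 76%.
2. **Section 15.** Replace exclusion from the study for unfilled forms with continued follow-up, so that a missed 4-week form does not cost the 8-week ODI. In the ITT analysis, analyse all available ODI data by randomised group.
3. **Section 16.** Make the primary between-group analysis of 8-week ODI adjust for baseline ODI, which Section 15 already collects. If Section 9 quotes power for this analysis, state the assumed correlation.

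The cost is a slightly less favourable stated power and small amendments to Sections 15 and 16. No additional patients or assessments are needed.
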